**PROTOCOL SYNOPSIS:****OTEZLA® IN COMBINATION WITH ADD-ON ENSTILAR®**

Study Title	A Single Center Study to Evaluate the Effectiveness and Safety of add on Enstilar® in Patients using OTEZLA® for Moderate to Severe Plaque Psoriasis
Sponsors	[name]
Study Objectives	
Primary Objective: To determine if adding Enstilar® topical therapy can help OTEZLA® partial responders to achieve PASI 75 by week 12.
 
Secondary Objective: To evaluate the efficacy of combining OTEZLA® and Enstilar®
 
To evaluate the safety of combining OTEZLA® and Enstilar®
 
To evaluate the subject quality of life when combining OTEZLA® and Enstilar®

Study Design	
50 adult patients with moderate to severe plaque psoriasis will be given OTEZLA® for 8 weeks.
 
At week 8, patients who achieved between PASI 25-74 response will receive 4 weeks of Enstilar® (calcipotriene and betamethasone dipropionate) Foam, 0.005%/0.064% in addition to continuing OTEZLA® therapy.
 
Patients who do not meet PASI 25 at week 8 will be discontinued from the study.
 
At week 12 (after 4 consecutive weeks of Enstilar® add on therapy), Enstilar® will be discontinued and these patients will continue Otezla® as monotherapy through week 16.
 
Patients who achieve PASI 75 at week 8 will remain enrolled on Otezla® monotherapy through week 16.

Study Centers	Single Center
Study Population	Adult male and female subjects with moderate to severe chronic plaque psoriasis
Main Inclusion Criteria	
Subjects must meet the following criteria to be enrolled in this study:
 
 
1. Male or female adult <math>\geq</math> 18 years of age;
 
2. Diagnosis of chronic plaque-type psoriasis
 
3. Moderate to severe plaque type psoriasis as defined at baseline by:
 

	
 
• PGA score of 3 or greater
 
• BSA affected by plaque-type psoriasis of 10% or greater
 
• PASI <math>\geq</math> 12
 
4. Able and willing to give written informed consent prior to performance of any study-related procedures
 
5. Must be in general good health (except for disease under study) as judged by the Investigator, based on medical history, physical examination, clinical laboratories, and urinalysis. (NOTE: The definition of good health means a subject does not have uncontrolled significant co-morbid conditions).
 

Main Exclusion Criteria	
Subjects who meet any of the following criteria will be excluded from participation in this study:
 
 
1. Other than psoriasis, any clinically significant (as determined by the investigator) cardiac, endocrinologic, pulmonary, neurologic, psychiatric, hepatic, renal, hematologic, immunologic disease, or other major disease that is uncontrolled.
 
2. Forms of psoriasis other than chronic plaque-type (e.g., Pustular erythrodermic and/or guttate psoriasis) or drug induced psoriasis
 
3. Subjects who previously used any biologic agent for psoriasis.
 
4. Use of oral systemic medications for the treatment of psoriasis within 4 weeks (includes, but not limited to, oral corticosteroids, methotrexate, acitretin and cyclosporine).
 
5. Patient used topical therapies to treat psoriasis on the hands and/or feet within 2 weeks of the Baseline Visit (includes, but not limited to, topical corticosteroids, vitamin D analogs, or retinoids).
 
6. Patient received UVB phototherapy within 2 weeks of Baseline.
 

Study Drug Dosage and Administration	
All patients will receive OTEZLA® 30mg twice daily at week 0 (baseline) through week 8. At week 8, patients who achieved between PASI 25-74 response will receive 4 weeks of add-on Enstilar® (calcipotriene and betamethasone dipropionate) Foam, 0.005%/0.064% once daily in addition to continuing OTEZLA® 30mg twice daily.
 
At week 12 (after 4 consecutive weeks of Enstilar® add on therapy), Enstilar® will be discontinued and patients will continue OTEZLA® 30mg twice daily as monotherapy through week 16.

	Patients who achieve PASI 75 at week 8 will remain enrolled on OTEZLA® 30mg BID monotherapy through week 16.
Study Endpoints	
Primary Endpoints:
 
PASI 75 at week 12 for patients in the OTEZLA® + Enstilar® combination arm.
 
Secondary Endpoints:
 
PASI 25-74 at week 8.
 
PASI, PGA, BSA, PGAxBSA and DLQI improvement at week 8
 
PASI, PGA, BSA, PGAxBSA and DLQI improvement at week 12
 
PASI PGA, BSA, PGAxBSA and DLQI improvement at week 16
 
Serious Adverse Events (SAE's)

Study Duration	
16 weeks
 
The subject may continue to participate in this study until one of the following occurs:
 
 
• Subject has not achieved PASI 25 at week 8
 
• The subject experiences a significant or serious adverse event related to study drug;
 
• Subjects who initially achieved PASI 75 at week 8 and lose response by week 12 may withdraw at their own request.
 
• Subjects who received Enstilar® add-on therapy for 4 weeks and have not achieved PASI 75 at week 12 may withdraw at their own request.
 
• The subject is not willing to continue participation in the study;
 
• Subject completes 16 weeks of study drug and evaluations
 
• The Sponsor decides to terminate the study for any reason.
 

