### **3.2 Rationale for Treating Plaque Psoriasis with OTEZLA® + Enstilar®**

OTEZLA® and Enstilar® are both effective in treating psoriasis. The pivotal OTEZLA® Phase III trials (ESTEEM) determined that apremilast was effective in treating moderate to severe plaque psoriasis. The primary endpoint at week 16 demonstrated significantly more apremilast-treated patients (33.1%) achieved the primary end point (PASI-75 at week 16) than did placebo patients (5.3%). Combination regimens that utilize a systemic agent with light therapy and/or a topical agent are becoming the standard of care in the United States and Europe, confirming the observation of Lebwohl et al in 2004, that the use of two or more therapies to treat patients with moderate to severe psoriasis seems to be the rule rather than the exception. Topical steroids play an important role in the long term management of psoriasis and data from the COBRA trial suggests that super potent topical corticosteroids are appropriate and well tolerated for use when added to existing therapeutic regimens i.e. phototherapy, systemic and biologic therapy. A post hoc analysis of the Phase 3 ESTEEM 1 trial of apremilast was conducted to assess the efficacy and safety of apremilast with and without topical therapies and/or UVB phototherapy. The analysis focused on the sub-group of patients who did not achieve PASI 75 at week 32. At week 52, more patients receiving topical therapy and/or phototherapy achieved PASI 75 than did patients with apremilast alone. This study is being conducted to determine if adding topical Enstilar® to Otezla® therapy can help patients who received a partial response at week 8 reach PASI 75 by week 12.

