## **4. STUDY OBJECTIVE**

To explore the effectiveness and safety of combining OTEZLA® and Enstilar® and to determine if add-on Enstilar® therapy can help partial responders at week 8 achieve PASI 75 at week 12.

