## **5. INVESTIGATIONAL PLAN**

### **5.1 Overall Study Design and Plan**

50 subjects affected with plaque psoriasis with body surface area greater than or equal to 10%, and physician's global assessment greater than or equal to 3 and PASI greater than or equal to 12 will receive OTEZLA® 30 mg twice daily for 8 weeks.

Patients who do not achieve at least a PASI 25 at week 8 will be discontinued from treatment and study procedures.

At week 8, subjects who have achieved a PASI 25-74 will receive Enstilar® (calcipotriene and betamethasone dipropionate) Foam, 0.005%/0.064% once daily for 4 weeks in addition to continuing OTEZLA® BID. These patients will then discontinue Enstilar® at week 12 and remain on OTEZLA® monotherapy through week 16.

Patients who achieve PASI 75 at week 8 will remain enrolled in the study and continue OTEZLA® 30mg BID through week 16. These subjects will not receive Enstilar® add-on therapy.

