## 8.2 Statistics

It is desired to enroll 50 patients based on the data from the Esteem trial which showed 55% of subjects achieved between a PASI 25- PASI 74 response at week 8, hence it is expected that 30-40 patients will fit the continuation criteria at week 8 and be followed through week 16.

The study will analyze data based on the non-responder imputation (NRI) method. This will be performed for each arm of the study (PASI 75 responders at week 8 and PASI 25-74 responders at week 8. Subjects who do not complete week 16 assessments will be classified as non-responders.

Since this is a pilot study with no formal hypothesis testing, statistical power/sample size is not formally presented in this protocol.

Analysis will be performed by the Investigator on proportion of subjects achieving Psoriasis Area Severity Index (PASI) 75 response at week 12

The investigator will also analyze PASI 25-74 at week 8, PASI, PGA, BSA, PGAxBSA and DLQI improvement at week 8, BSA, PGA and BSA x PGA and DLQI improvement at week 12. PASI, BSA, PGA, BSA x PGA and DLQI at week 16. This analysis will be done separately for both cohorts (PASI 75 responders at week 8 and PASI 25-74 responders at week 8) using summary statistics. The Investigator will also analyze SAE's by cohort.

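### The primary objective asks whether adding Enstilar helps, but all partial responders receive it and the planned uncontrolled week-12 PASI 75 proportion cannot answer that question

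*Combined protocol and SAP*

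**What the plan says.** The primary objective in the synopsis is "To determine if adding Enstilar® topical therapy can help OTEZLA® partial responders to achieve PASI 75 by week 12". Section 3.2 puts the purpose the same way ("This study is being conducted to determine if adding topical Enstilar® to Otezla® therapy can help patients"). Section 4 opens with an exploratory aim for the combination, then adds "to determine if add-on Enstilar® therapy can help partial responders at week 8 achieve PASI 75 at week 12".

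Section 5.1 assigns treatment after week 8 by response alone: "subjects who have achieved a PASI 25-74 will receive Enstilar", with OTEZLA continued. Subjects below PASI 25 leave the study. Subjects at PASI 75 stay on OTEZLA alone. No partial responder stays on OTEZLA alone over weeks 8 to 12.

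The synopsis defines the primary endpoint as "PASI 75 at week 12 for patients in the OTEZLA® + Enstilar® combination arm". The planned analysis in section 8.2 is "Analysis will be performed by the Investigator on proportion of subjects achieving Psoriasis Area Severity Index (PASI) 75 response at week 12". That section calls the study a pilot without formal hypothesis testing and uses summary statistics separately by cohort. It applies non-responder imputation, under which anyone who does not complete the week-16 assessments is a non-responder. Section 8.2.1 allows a separate statistical plan at the sponsor-investigator's discretion.

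**The concern.** Whether adding a treatment helps is a question about a difference: response with the add-on against response without it in the same kind of patient. The plan observes only the first of these. The cohort starts at 0% PASI 75 by selection, so any crossing of the cut between weeks 8 and 12 raises the rate, whether it comes from Enstilar, from continued OTEZLA or from variation in PASI around the cut.

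The rationale shows the kind of evidence the question needs. The post hoc analysis cited in section 3.2 set add-on treatment against apremilast alone: "At week 52, more patients receiving topical therapy and/or phototherapy achieved PASI 75 than did patients with apremilast alone". This study has no matching group among its partial responders.

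At stake is the primary conclusion. A moderate week-12 rate could be reported as showing that Enstilar helps when the data cannot separate its contribution. Without an interval, the report would also hide how uncertain the rate is.

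**Working it through.** **1. Is there a comparator anywhere in the plan?**
- Subjects below PASI 25 at week 8 are discontinued, so they have no week-12 outcome on treatment.
- Subjects at PASI 75 at week 8 already meet the endpoint when the add-on period starts, so they are not a control for subjects who do not. Section 8.2 summarises the two cohorts separately.
- Section 5.4 speaks of randomisation, but all 50 subjects start the same regimen.
- Section 8.2 names no historical rate or threshold.

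There is none.

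**2. Size of the add-on cohort.** Inputs from section 8.2: 50 enrolled and 55% with PASI 25-74 at week 8.
- 50 × 0.55 = 27.5, so about 27 subjects.
- Section 8.2 expects 30-40 to meet the continuation criteria. The 55% alone does not reproduce that. It could hold if week-8 PASI 75 responders are counted too, but the text does not say so. The argument here does not depend on which reading is right.

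**3. What would happen on OTEZLA alone?** Inputs: 33.1% PASI 75 at week 16 on apremilast (section 3.2) and 55% partial responders at week 8 (section 8.2). The week-8 PASI 75 rate is not given; call it x. Assume that all new responders come from the partial responders and that no week-8 responder is lost. Then week-16 conversion = (0.331 − x) / 0.55.
- If x = 0.331: 0 / 0.55 = 0%.
- If x = 0: 0.331 / 0.55 = 60.2%.
- If the gain from week 8 to week 16 were linear, half would be reached by week 12: 0% to 30.1%.

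The linear shape is an assumption; an earlier gain would put the week-12 figure higher. At the top of the linear range, 0.301 × 27 = 8.1 subjects would reach PASI 75 by week 12 with no Enstilar effect at all. At the bottom, none would.

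**4. Precision of the single proportion.** Exact (Clopper-Pearson) 95% limits: lower = the 2.5% quantile of Beta(x, n − x + 1), upper = the 97.5% quantile of Beta(x + 1, n − x), where x is now the number of responders.

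| Responders / n | Rate | Exact 95% CI | Width (points) |
|---|---|---|---|
| 8/27 | 29.6% | 13.8-50.2% | 36.4 |
| 13/27 | 48.1% | 28.7-68.1% | 39.4 |
| 12/40 | 30.0% | 16.6-46.5% | 29.9 |
| 20/40 | 50.0% | 33.8-66.2% | 32.4 |

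The rows for n = 40 take the upper end of the section 8.2 expectation as if all were partial responders. The interval is still about 30 points wide or more.

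**5. Does the planned proportion equal the week-12 rate?** Not if the imputation rule is read literally. A subject who reaches PASI 75 at week 12 but misses week 16 is counted as a failure. The reported figure would then be response at week 12 combined with completion of week 16.

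**The case against.** The strongest reply is that this is a declared pilot without hypothesis testing, that section 4 speaks of exploring, and that the endpoint is a plain rate in one cohort. On that view the objective is loosely worded and the design is what a pilot should be. Much of this stands. The fault lies between the wording of the objective and what the design can show; no test has failed, and a pilot need not have a control arm. But the exploratory wording in section 4 attaches to the combination, and the same sentence keeps the question about the add-on. Pilot status fits an estimation objective. It does not let an uncontrolled rate settle whether the add-on helps, and it is no reason to leave out the interval.

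It can also be said that the OTEZLA-only weeks 12 to 16 act as a control, or that a later plan may add one. No such contrast is planned. Carry-over, continuing OTEZLA response and the permitted withdrawal of subjects not at PASI 75 at week 12 would confound it. The separate plan is optional and unspecified.

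A reader might go further and infer that some count, such as 13/27, would be high enough to rule out OTEZLA alone. The documents do not support a threshold of that kind. The lower limit for 13/27 is 28.7%, below the 30.1% that the linear assumption allows, and linearity is itself not established.

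**Conclusion.** The point holds as a mismatch between objective and analysis. Followed as written, the plan yields the week-12 PASI 75 rate on OTEZLA plus Enstilar in partial responders, not the contribution of Enstilar. This follows from the text and needs no numerical assumption.

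The size of the possible OTEZLA contribution is unknown. The 0 to about 60% (week 16) and 0 to about 30% (week 12) figures are bounds under the stated assumptions, not estimates, and a narrower range would need a week-8 PASI 75 rate that the documents do not give. The imprecision is firmer: about 36 to 39 points of interval width for 8 to 13 responders among 27.

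A reader might infer that Enstilar adds nothing, or that the study has no value. Neither follows. The combination rate is a legitimate pilot result if it is labelled as such.

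**What to change.** 1. In the synopsis, section 3.2, section 4 and section 8.2, restate the primary objective as estimating the week-12 PASI 75 rate with add-on Enstilar in subjects with PASI 25-74 at week 8.
2. In section 8.2, report that rate with an exact (Clopper-Pearson) 95% confidence interval, with all subjects who enter the add-on cohort as the denominator.
3. For this endpoint, classify non-response by the week-12 assessment, not by completion of week 16.
4. State that, without a concurrent control, the rate is not by itself evidence of an Enstilar effect.

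A minor consistency edit can be made at the same time: the section 8.2 list for week 12 leaves out PASI improvement, which the synopsis lists as a secondary endpoint.

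The cost is wording in four places, one interval and one clarified rule. No subjects, visits or tests are added. The downside is that the study no longer claims to settle whether Enstilar helps, and the published interval will be visibly wide.

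### Analysed by cohort as section 8.2 states, the week-8 PASI 25-74 endpoint is 100% and 0% by construction and never counts subjects below PASI 25

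*Combined protocol and SAP*

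**What the plan says.** The Synopsis (Study Endpoints) gives "PASI 25-74 at week 8" as the first secondary endpoint, without a denominator. Section 8.2 repeats it: "The investigator will also analyze PASI 25-74 at week 8". It then lists the improvement measures at weeks 8, 12 and 16, and closes: "This analysis will be done separately for both cohorts (PASI 75 responders at week 8 and PASI 25-74 responders at week 8". Only descriptive summaries are planned.

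The same band decides who receives Enstilar at week 8 (Synopsis, 5.1 and 5.6). Subjects above it form a separate group: "Patients who achieve PASI 75 at week 8 will remain enrolled on OTEZLA® 30mg BID monotherapy through week 16". Subjects below it leave: "Patients who do not meet PASI 25 at week 8 will be discontinued from the study".

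For missing data, 8.2 applies non-responder imputation to each of the two groups: "Subjects who do not complete week 16 assessments will be classified as non-responders".

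The only figures tied to the band are in 8.2. Planned enrolment is 50, and the earlier trial cited in support of that number "showed 55% of subjects achieved between a PASI 25- PASI 74 response at week 8". From this, the plan expects 30-40 subjects to meet the continuation criteria.

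Neither the Synopsis nor 8.2 gives an all-treated denominator for this endpoint, or lists a week-8 proportion at PASI 25 or better or at PASI 75 or better.

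**The concern.** The variable being summarised is the one that defines the cohorts, so a summary within cohort carries no information. The cohort structure also has no place for subjects below PASI 25 at week 8, so the analysis as written does not count those who did least well on OTEZLA alone.

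There is a second, separate difficulty. Even over all treated subjects, a band with an upper limit scores a PASI 80 subject and a PASI 10 subject alike, as not meeting the endpoint. The proportion is therefore not ordered by benefit. At stake is how the first 8 weeks are reported: this is the only responder-type endpoint listed for week 8, and a reader could take a higher or lower value as better or worse efficacy when it shows neither by itself.

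**Working it through.** **Inputs (section 8.2).** N = 50; proportion in the band p = 0.55; expected to continue = 30-40. No week-8 PASI 75 rate is given.

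**1. The plan's own figure.** Expected number in the band = N × p = 50 × 0.55 = 27.5. This does not reproduce 30-40. PASI 75 responders also continue to week 16. If they are included, the range requires 30 − 27.5 = 2.5 to 40 − 27.5 = 12.5 such subjects, that is 2.5/50 = 5% to 12.5/50 = 25%. That is an assumption about what 30-40 counts, and nothing in steps 2 to 4 depends on it.

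**2. By cohort, as written.** Let n1 be the number in the PASI 25-74 cohort and n2 the number in the PASI 75 cohort.
- PASI 25-74 cohort: n1/n1 = 100%.
- PASI 75 cohort: 0/n2 = 0%.
- Subjects below PASI 25: in neither numerator nor denominator.

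**3. If the week-16 rule is applied to week 8.** With a share d of the PASI 25-74 cohort not completing week 16, the first figure becomes 1 − d. For assumed d of 10%, 20% and 30% it is 90%, 80% and 70%. It then measures later dropout, not week-8 response. The 0% does not change.

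**4. Over all 50 (a denominator the plan does not state).** Start from 27.5/50 = 55%.

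| Change, all else equal | Number in band | Endpoint |
|---|---|---|
| None | 27.5 | 55% |
| 5 subjects improve from the band to PASI 75 | 22.5 | 45% |
| 5 subjects improve from below PASI 25 into the band | 32.5 | 65% |

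Both changes are improvements, and the endpoint moves in opposite directions. The last row assumes that at least 5 of the 22.5 subjects outside the band are below PASI 25.

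The same value also fits very different results. Take 28 of 50 in the band (27.5 rounded up): 56%, exact 95% confidence interval 41% to 70%. The splits of the other 22 are illustrative.

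| Below 25 | 25-74 | 75 or more | Endpoint | PASI 25 or better | PASI 75 or better |
|---|---|---|---|---|---|
| 22 | 28 | 0 | 56% | 28/50 = 56% | 0% |
| 10 | 28 | 12 | 56% | 40/50 = 80% | 12/50 = 24% |
| 0 | 28 | 22 | 56% | 50/50 = 100% | 22/50 = 44% |

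The cumulative proportions separate these cases; the band alone does not.

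**The case against.** The strongest reply is that the endpoint was never meant to measure efficacy. The stated objectives concern add-on and combination therapy, and the band is the gate for Enstilar. Read that way, it is the share of subjects eligible for the add-on, for which a closed band is the right definition. This stands, and it is why the band should be kept. It does not rescue the by-cohort analysis, because a share eligible for add-on needs an all-treated denominator.

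A second reply is that the by-cohort sentence follows a long list, makes sense for the improvement measures, and was probably not intended for the variable that defines the cohorts. Loose drafting is a plausible explanation. But the sentence covers the list as it stands, and nothing elsewhere supplies another rule; section 8.2.1 says only that a separate plan may add detail.

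A third is that reported cohort sizes would let a reader recover most of the split. That is largely right. Given both sizes and the number enrolled, the remainder are subjects below PASI 25 or without a week-8 assessment. It would therefore be wrong to infer that a reader could not tell how many subjects had a partial response and how many had a full one. What is missing is an instruction to report the figures this way.

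A reader might also infer that the endpoint falls whenever OTEZLA works better. The documents do not support that: improvement from below PASI 25 raises it. Not ordered by benefit is accurate; falling with benefit is not.

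Finally, this is a pilot without formal hypothesis testing, and week-8 improvement in PASI, PGA, BSA, PGAxBSA and DLQI is also listed. Both points limit the weight of the concern. The improvement measures are, however, reported within the same two cohorts, so they too leave out subjects below PASI 25.

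**Conclusion.** The point holds in a limited form. Section 8.2 read literally returns 100% and 0% for this endpoint and excludes subjects below PASI 25. This follows from the definitions and needs no numerical assumption; the only qualification is the dropout effect if the week-16 rule is carried back to week 8. Over all treated subjects the 25-74 share is a valid measure of eligibility for the add-on, but not a measure of efficacy: from 55%, equally sized improvements of 5 subjects can give 45% or 65%.

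The consequence is for description and interpretation only. The primary endpoint, PASI 75 at week 12, is untouched, and no error rate is involved. It would go too far to conclude that the plan cannot describe week-8 efficacy at all, since the improvement measures exist. Likewise, a week-8 PASI 75 rate of 5% to 25% is not stated in the plan; it follows only if 30-40 is assumed to include PASI 75 responders, and must be labelled as such.

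**What to change.** In the Synopsis and section 8.2:

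- Take this endpoint out of the list analysed separately by cohort.
- Report week-8 response over all subjects who started OTEZLA, with a missing week-8 PASI counted as not responding, in three categories: below 25, 25-74, and 75 or more.
- Add the cumulative proportions at PASI 25 or better and PASI 75 or better, on the same denominator.
- Keep the 25-74 share, labelled as the size of the add-on cohort.
- State that the week-16 completion rule does not apply to these week-8 figures.
- If a PASI 75 rate is derived from the 30-40 figure, label it an assumption.

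The cost is a small rewording of one secondary endpoint and one table. The Schedule of Events (8.3) already has PASI at baseline and week 8, so no visit, subject or treatment rule changes.

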## **6 ADVERSE EVENTS**

An adverse event (AE) is any noxious, unintended, or untoward medical occurrence occurring at any dose that may appear or worsen in a subject during the course of a study. It may be a new intercurrent illness, a worsening concomitant illness, an injury, or any concomitant impairment of the subject's health, including laboratory test values (as specified by the criteria below), regardless of etiology. Any medical condition that was present prior to study treatment and that remains unchanged or improved should not be recorded as an AE. If there is a worsening of that medical condition this should be considered an AE. A diagnosis or syndrome should be recorded on the AE page of the Case Report Form rather than the individual signs or symptoms of the diagnosis or syndrome.

All AEs will be recorded by the Investigator(s) from the time of signing the informed consent through the end of the designated follow-up period.

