## Classification of severity

For both AEs and SAEs, the investigator(s) must assess the severity of the event. The AEs will be evaluated for severity according to the following scale:

Grade 1 = Mild

Grade 2 = Moderate

Grade 3 = Severe

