### 8.3 Schedule of Events

Procedure	Screening	BASELINE	Week4	Week 8	Week 12	Week 16
Informed Consent	X					
Demographics/Medical History	X	X				
Inclusion/Exclusion	X	X				
Physical Exam	X	X		X	X	X
Concomitant Medications	X	X	X	X	X	X
Adverse Events	X	X	X	X	X	X
Urine Preg Test	X	X				X
PASI	X	X		X	X	X
BSA	X	X		X	X	X
PGA	X	X		X	X	X
DLQI		X		X	X	X
Vital Signs	X	X		X	X	X
IP dispensing/accountability		X	X	X	X	X

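### Safety of the combination is an objective, but the only planned safety analysis is SAEs by week-8 cohort, so the objective is answered only in part

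*Combined protocol and SAP*

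**What the plan says.** The Synopsis gives as a secondary objective "To evaluate the safety of combining OTEZLA® and Enstilar", and Section 4 has the same aim: "To explore the effectiveness and safety of combining OTEZLA® and Enstilar". The Study Endpoints row of the Synopsis holds one safety item, the last of the secondary endpoints: "Serious Adverse Events (SAE's". Section 8.2 gives safety one sentence: "The Investigator will also analyze SAE's by cohort". The cohorts are those used for the efficacy summaries: "This analysis will be done separately for both cohorts (PASI 75 responders at week 8 and PASI 25-74 responders at week 8". No time window or treatment period is attached to the SAE analysis.

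Collection is much wider than analysis. Section 6 states: "All AEs will be recorded by the Investigator(s) from the time of signing the informed consent". Under Classification of severity it adds: "For both AEs and SAEs, the investigator(s) must assess the severity of the event". Causality is also classified, as suspected or not suspected. In the Section 8.3 schedule the row "Adverse Events" is marked at all six visits. Section 8.2.1 allows a separate statistical plan at the sponsor-investigator's discretion but commits to no content.

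**The concern.** There are two gaps between the objective and the analysis.

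- **Which events are summarised.** Non-serious AEs, AEs suspected to be drug-related, and AEs that lead to stopping OTEZLA or Enstilar appear in no endpoint and no planned summary. In a cohort this small, these are the safety data most likely to contain any information.
- **Which treatment the events belong to.** The cohorts are defined by response at week 8, not by treatment at the time of the event. The add-on cohort takes both drugs only in weeks 8-12. With no window, an SAE from weeks 0-8, before any Enstilar, can be counted in the add-on cohort. Section 5.5.1.2 shows how this could happen: it describes severe gastrointestinal events with OTEZLA that cluster early in treatment and sometimes led to hospital admission, which is an SAE criterion in Section 6.

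At stake is a safety result for the combination that rests on very few events, some of which may have occurred on OTEZLA alone, while the tolerability data stay unsummarised.

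**Working it through.** **The plan's own figure.** Section 8.2 enrols 50 and cites 55% with a PASI 25-74 response at week 8, then expects 30-40 to continue. 0.55 × 50 = 27.5, about 28, so 30-40 does not follow from the 55% alone. It would follow if week-8 PASI 75 responders, who also continue, made up (30 − 27.5)/50 = 5% to (40 − 27.5)/50 = 25% of those enrolled, but the documents give no such rate. I use 28 add-on subjects and show 40 as an upper case.

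**Exposure to the combination.** 28 × 4 weeks = 112 person-weeks. For a subject who completes week 16, the combination is 4/16 = 25% of follow-up. For one who leaves at week 12, as the Study Duration row of the Synopsis permits for add-on subjects without PASI 75, it is 4/12 = 33%. A cohort count with no window would thus draw 67% to 75% of its time from OTEZLA alone.

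**What SAEs alone can show.** The documents give no SAE rate, so the risks below are assumptions for the combination period. P(at least one event in n subjects) = 1 − (1 − p)^n.

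| Assumed SAE risk p | n = 28 | n = 40 |
|---|---|---|
| 0.5% | 13% | 18% |
| 1% | 25% | 33% |
| 2% | 43% | 55% |
| 5% | 76% | 87% |

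For example, 1 − 0.99^28 = 0.245.

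**What all AEs could show.** The same formula with n = 28 and assumed AE incidences of 5%, 10% and 20% gives 76%, 95% and 99.8%.

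**Collected against analysed.**

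| Item | Collected | Summary planned |
|---|---|---|
| SAEs | Yes, with start and stop dates, relationship and action taken (Section 6) | Yes, by cohort, no period (8.2) |
| Non-serious AEs | Yes, every visit (6, 8.3) | None |
| Severity grade and causality, all AEs | Yes (6) | None |
| AEs that stop a drug | Stopping rules exist (5.5.1.5, 5.5.2.4) | None |
| Onset date and action taken, non-serious AEs | Not stated | None |

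**The case against.** The strongest reply is that this is a pilot with no formal hypothesis testing, that safety is secondary and exploratory, and that the AE data will exist, so tables can be added before analysis. This stands as an argument about priority: the primary endpoint and treatment assignment are untouched. It does not remove the gap. Descriptive AE tables need no hypothesis test, and Section 8.2 already plans summary statistics for efficacy.

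Several stronger readings are tempting, and the documents do not support them.

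- **That SAEs will be pooled over the whole study.** This is an inference from the missing window. Section 8.2 does not say so, and Section 6 requires start and stop dates for each SAE, so each one can be placed in a treatment period. With few SAEs, misattribution is a limited risk.
- **That the collected AEs are never used, or that the objective cannot be answered at all.** AEs drive decisions to stop treatment or leave the study (Synopsis, Study Duration; Sections 5.5.1.5, 5.5.2.4 and 5.6.10). SAEs cover part of safety, and the Section 6 definition includes important medical events.
- **That the trial will most likely see no SAEs.** Without a stated rate this cannot be claimed. The assumed range gives 13% to 76% for at least one in 28.
- **That zero SAEs would be uninformative because SAEs were chosen.** Zero in 28 leaves an exact two-sided 95% upper limit of 1 − 0.025^(1/28) = 12.3%, but this reflects n = 28 and holds for any type of event.
- **That the depression figures in Section 5.5.1.2 prove the point.** They compare OTEZLA with placebo and do not bear on the combination. Taking 12/920 as a 16-week risk at a constant rate, 28 × 12/920 × 4/16 = about 0.09 events would be expected in the combination weeks, so counting all AEs would probably show none either.

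One objection also limits the fix. Onset date and action taken are documented only for SAEs, so it cannot be assumed that every AE can already be tabulated by treatment at onset.

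**Conclusion.** The point holds: as written, the analysis addresses the objective on safety of the combination only in part. Endpoint and analysis section agree on SAEs only, so this is the plan and not a slip in one place, and the optional further plan in Section 8.2.1 does not fill the gap. In size, about 28 subjects contribute about 112 person-weeks of combination treatment, with about a 25% chance of seeing one SAE at an assumed 1% risk (13% to 76% over assumed risks of 0.5% to 5%). This rests on the 55% response share in Section 8.2, full completion of the four add-on weeks, and SAE and AE rates that the documents do not give.

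It is a cheap improvement, recommended rather than must-fix. Even with it, safety remains descriptive: the week-8 PASI 75 responders are selected by response and are not a randomised comparator.

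**What to change.** - In the Synopsis, Study Endpoints, and in the last sentence of the Section 8.2 analysis paragraph, replace SAEs alone with all AEs and SAEs.
- Summarise the number and proportion of subjects with events by severity grade, by suspected relationship, and for AEs leading to stopping OTEZLA or Enstilar.
- Tabulate by treatment at onset: OTEZLA alone in weeks 0-8; OTEZLA + Enstilar in weeks 8-12; OTEZLA alone in weeks 12-16; and OTEZLA alone in weeks 8-16 for week-8 PASI 75 responders. Keeping weeks 12-16 apart from weeks 0-8 also separates time after Enstilar from time before it.
- Confirm that the AE page records onset date and action taken for every AE. If it does not record onset, assign the period from the visits at weeks 8, 12 and 16, where treatment changes.

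The cost is two changes of wording, a few descriptive tables and possibly two AE-page fields. No new visit or procedure is needed.
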